8.4 Study Medications

In this study, Xlucane 0.5 mg (0.05 mL of 10 mg/mL ranibizumab) will be administered by ophthalmic IVT injection (only) once every 4 weeks (approximately 28 days/monthly) in the study eye for 12 months in subjects with wAMD who are randomized to receive Xlucane.

Lucentis® 0.5 mg (0.05 mL of 10 mg/mL ranibizumab) will also be administered by ophthalmic IVT injection (only) once every 4 weeks (approximately 28 days/monthly) in the study eye for 12 months in subjects with wAMD who are randomized to receive Lucentis®.

The study medication (Xlucane & Lucentis®, respectively) should be administered only by qualified ophthalmologists experienced in IVT injections.

The IVT injection procedure should be carried out under controlled aseptic conditions, which include the use of sterile gloves, a sterile drape, and a sterile eyelid speculum (or equivalent). Adequate anesthesia and a broad-spectrum microbicide should be given prior to the injection.

Approximately 30 minutes following the IVT injection, subjects should also be monitored for elevation in IOP using Goldmann tonometry. Noncontact tonometry is allowed but if IOP is greater than 30 mm Hg, the result should be confirmed by applanation tonometry (eg, Goldmann, Tonopen, Icare) within the next 30 minutes. Subjects should also be monitored onsite for (at least 60 minutes) and instructed to report any symptoms suggestive of endophthalmitis without delay following the injection.

Each vial should only be used for the treatment of a single eye (ie, the study eye). Lucentis® prefilled syringes may be used if needed (eg, if vials are not available).

8.4.1 Identity of Study Medication

Based on the design of this protocol, the Principal Investigator (PI) **MUST** oversee proper separation and delegation of unmasked study roles and responsibilities. To ensure the masking of each randomized subject, the PI must delegate tasks to an unmasked treating investigator and ample unmasked support staff to execute protocol instructions.

Xlucane/ Lucentis® for IVT injection is supplied as single-use vial designed to deliver 0.05 mL of 10 mg/mL ranibizumab. (Lucentis® prefilled syringes may be used if needed [eg, if vials are not available].) The details of the study medications are given in [Table 3](#). All study drug will be imported according to the relevant regulatory requirements. **It must be noted that EU-Lucentis® is not FDA approved and is therefore considered an investigational new drug in the United States.**

Table 3 Study Medication Details

Study Medication	Dosage Form and Strength	Manufacturer
Xlucane	Supplied as single-use, 2-cc glass vial containing 2.3 mg of proposed ranibizumab biosimilar in 0.23 mL solution designed to deliver 0.05 mL of 10 mg/mL proposed ranibizumab biosimilar, by intravitreal injection.	Xbrane Biopharma [name] [name] Sweden
EU-licensed Lucentis®	Supplied as single-use, 2-cc glass vial containing 2.3 mg of ranibizumab in 0.23 mL solution designed to deliver 0.05 mL of 10 mg/mL ranibizumab, by intravitreal injection.	Novartis Pharma Stein AG [name] [name] Switzerland

8.4.1.1 Xlucane

Xlucane is a sterile, colorless solution in a single-use glass vial. Xlucane is supplied as a sterile solution in a single-use container designed to deliver a 0.05 mg/mL of 10 mg/mL ranibizumab.

Xlucane is for IVT injection only. Keep vial(s) refrigerated at 2°-8°C (36°-46°F). Do not freeze. Protect vial(s) from direct sunlight.

There are no human- or animal-derived materials used in the Xlucane DS and Xlucane DP manufacturing process. A Master Cell Bank (MCB) has also been established for the DS manufacturing process.

8.4.1.2 Lucentis® (ranibizumab injection)

Xbrane has made a thorough physicochemical assessment, of Lucentis® to provide information for defining the quality target product profile. The choice of analytical methods is based on FDA Guidance, the EMA guideline, ICH Q5E, advice from the CHMP, and data available in the public domain for the reference product.^{5,15,16,17}

The quality target product profile (QTPP), has been determined by analysis and characterization of Lucentis® lots (SL732 expiry date 09-2019; ST601 expiry date 11-2019; SR124 expiry date 01-2020; 3179575 expiry date 01-2020; SJ836 expiry date 06-2019; SK351 expiry date 08-2019; SX444 expiry date 08-2020; and B0014801 expiry date 08-2020). The QTPP is continuously updated with data from sourced and analyzed Lucentis® batches and it will serve as a basis for similarity evaluation of Xlucane GMP batches (manufactured for the phase III clinical study) to Lucentis®.

Lucentis® is a sterile, colorless to pale yellow solution in a single-use prefilled syringe or a single-use glass vial. Lucentis® is supplied as a preservative-free, sterile solution in a single-use container designed to deliver 0.05 mL of 10 mg/mL Lucentis® (0.5 mg dose prefilled syringe or vial) aqueous solution with 10 mM histidine HCl, 10% α,α -trehalose dihydrate, 0.01% polysorbate 20, pH 5.5.

Lucentis® should be refrigerated at 2°-8°C (36°-46°F). DO NOT FREEZE. Do not use beyond the date stamped on the label. Protect Lucentis® prefilled syringes and vials from light and store in the original container until time of use. Do not open Lucentis® prefilled syringe sealed tray until time of use.

8.4.2 Packaging and Labeling

All investigational products provided by the Sponsor are supplied as individual kits. Study medication will be packaged and labeled at a central packaging facility. All packaging and labeling operations will be performed according to Good Manufacturing Practice for Medicinal Products and the relevant regulatory requirements.

Each study kit (1x white cartons) will contain either one 2-cc glass vial of Xlucane or one 2-cc glass vial of Lucentis®. The Xlucane and Lucentis® single-use containers will be appropriately labeled. A clinical label will be placed on cartons and rendered tamper evident. Each kit will have unique identification number.

Sites are to dispense the appropriate kit per IWRS information upon subject randomization and at each subsequent visit. Each study kit will have appropriate labeling information according to regulatory requirements.

Site must contact the CRA in case of any questions.

The study medication kits must be stored under refrigeration at 2°-8°C (36°-46°F) at all times. The product should be kept in the original carton to protect from light until the time of use. Do Not Freeze. Do not use beyond the expiry date which is stated on the carton/vial. Do not use any kit if it is damaged. Study medication vials should be used once only and any unused portion left in the vials/syringes should not be considered for use.

In case prefilled syringes are used as a contingency, additional documentation will be provided to investigators/sites and regulatory authorities as needed in compliance with country regulatory requirements.

8.4.3 Randomization

The receipt and review of the lab report is necessary before randomizing a subject. Upon confirmation of eligibility for a given subject to participate in the study, a unique randomization number for that subject will be assigned via an IWRS. The IWRS will be accessed immediately by study site personnel after confirmation of the subject's eligibility has been recorded. The randomization number for a given subject will be used to identify the study drug that will be administered to that subject.

The randomization scheme will automatically ensure that the study drug assignment for a given subject is random and that an overall 1:1 ratio of assignments to each of the 2 study drug treatments is approximated.

In addition, the randomization scheme will include the following stratification parameters to ensure balanced distribution of assignment to the 2 treatments: eye color (light iris vs dark iris), geographical region where enrolled and the BCVA letters at Baseline (55 or lower, 56 to 65, 66 or higher). Permuted random blocks within each stratification combination will be used to ensure the 1:1 ratio within each combination.

An independent biostatistician will create the randomization scheme, which will remain unavailable to all other masked individuals, until after study completion and subsequent locking of the study database.

Once a randomization number has been assigned, that number must not be used again for any other subject (eg, when a subject is withdrawn from the study, that subject's randomization number must not be used again for any other subject).

8.4.4 Selection of Doses in the Study

The dose and route of administration for Xlucane will be identical to that of Lucentis®. The recommended dose for Lucentis® is 0.5 mg (0.05 mL of 10 mg/mL ranibizumab) given as a single IVT injection every 4 weeks/monthly.

8.4.5 Selection and Timing of Dose for Each Subject

Subjects will be randomized by IWRS to receive 13 doses of either Xlucane or Lucentis® in the study eye, once every 4 weeks/monthly over 52 weeks. Proper aseptic injection technique should always be used when administering the IVT injections.

The minimum interval between 2 consecutive injections/doses should not be less than 4 weeks minus the visit window interval of the scheduled visit.

For example, Visit 3 (Week 2) to Visit 5 (Week 8) allow -2 day window, therefore the minimum interval between two consecutive injections between these visits can be 26 days.

Visit 6 (Week 12) to Visit 16 (Week 52) allow a -5 day window, therefore the minimum interval between two consecutive injections between these visits can be 23 days.

If a visit is outside the protocol defined visit window, should be considered as 'Late Visit or Out Of Window visit' and must be entered in the CRF as a protocol deviation (PD). Visits that are delayed for more than 14 days from the scheduled visit date, should be considered as 'missed' visits. The next visit should be scheduled in consideration of the protocol defined interval as much as possible and as per medical judgement of the investigator.

The study is expected to complete no later than one year or 12 months (+7 days) from the date of the last patient randomized into the study. This will be considered as the study end date and will be communicated once the last patient has been randomized.

Patient visits should be scheduled as per the protocol and within stipulated visit windows to ensure all patients complete the study and have the EOT (Visit 16) scheduled within the study end date.

If due to any reason it is not possible to complete all remaining visits for any patient within the study end date, an early termination visit must be scheduled and EOT procedures completed as per [Section 8.1.1](#)

8.4.6 Masking

Due to the study objectives, the identity of the study treatment assignments will not be known to subjects. Additionally, except for the site designees who are unmasked for the purpose of preparing and administering the study treatments, other research staff will also be masked. Masked study team members will perform efficacy assessments.

There will be no overlap between the masked and unmasked staff members. Access to the randomization codes will be strictly controlled.

The study medications will have caps/stoppers of differing colors and length; however, they will be packaged and labeled in identical outer cartons. Therefore, sites must have the following unmasked team members and their designated back-ups:

- Unmasked personnel to prepare syringes for IVT injection and provide to the unmasked injector, and complete study drug accountability.
- Unmasked injector to perform injection and safety assessments immediately after the injections (but not to participate in the efficacy assessments).

- There will also be masked and unmasked clinical research associates (CRAs) available for the same site. Unmasked CRAs will monitor study drug accountability.

Randomization information for any particular subject may be made available to the investigator only in the event of a medical emergency or an AE that necessitates identification of the study drug for the welfare of that participant. Masking codes should only be broken in emergency situations for reasons of participant safety. Whenever possible, the investigator(s) should always consult with the medical monitor and the Sponsor prior to breaking the masking.

When the masking code is broken, the reason must be fully documented. The reporting requirements for unmasking are the same for reporting an SAE. See also [Section 10.1.4.2.1 Serious Adverse Events](#).

When all subjects have completed their 6-month assessments, an *unmasked* analysis of efficacy (ie, equivalence) and safety endpoints as well as PK and immunogenicity will be performed. The aim of the *unmasked* analysis is to initiate the submission of the application for marketing authorization as agreed with the European Medicines Agency. This analysis will not affect the further conduct of the study.

8.4.7 Prior and Concomitant Therapy

The use of any concurrent medication, prescription or over-the-counter, is to be recorded on the subject's source document and corresponding electronic data capture form (eg, eCRF) along with the reason the medication was taken.

Drug interaction studies have not been conducted with Lucentis®.

During the study, subjects may **not** receive any standard or investigational agents for treatment of their AMD in the study eye other than study treatment until they have completed the final or early termination visit assessments. This includes medications administered locally (eg, IVT by juxtascleral or periorbital routes), as well as those administered systemically with the intent of treating the fellow eye. Vitamins and dietary supplements are allowed.

In case the fellow eye develops AMD or other medical condition during the study, it is expected that the fellow eye may be treated locally (eg, IVT by juxtascleral or periorbital routes), with standard of care therapy per local clinical practice first.

If anti-VEGF therapy is necessary, it is recommended to start it no earlier than after the last PK assessment and to perform the fellow eye IVT procedures in the interval between the study drug injections.

Any other medications that are considered necessary for the subject's welfare and that are not expected to interfere with the evaluation of the study medication may be given at the discretion of the Investigator, with the **exceptions** noted below:

- Any systemic treatment or ocular treatment with an investigational agent
- Systemic anti-VEGF therapy

If the permissibility of any medication/treatment is in question, please contact the medical monitor. Ocular surgery to the study eye should be delayed until the subject completes the study, if possible and safe.

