Efficacy data (ROW): Biosimilarity will be concluded if the two-sided 95% confidence interval (CI) for the difference in mean change in BCVA at Week 8 between the Xlucane and Lucentis[®] is confined within the equivalence margin of ± 3.5 letters.

Efficacy data (US FDA): Biosimilarity will be concluded if the two-sided 90% confidence interval (CI) for the difference in mean change in BCVA at Week 8 between the Xlucane and Lucentis® is confined within the equivalence margin of ± 3.5 letters.

The difference in the approach around the confidence interval is based on the regulatory requirement in the United States (90% CI) and the rest of the world (95% CI), as agreed with the relevant regulatory authorities.

The change in BCVA letters at Week 8 compared to Baseline using the ETDRS protocol will be analyzed using a mixed model for repeated measures (MMRM). An MMRM approach will be fitted with geographical region of the country where enrolled, visit, eye color (light iris vs dark iris), treatment, and treatment-by-visit interaction as fixed effects, with the Baseline BCVA letters and Baseline BCVA letters-by-visit interaction as covariates. The treatment differences from the model at Week 8 will be evaluated and a 95% or 90% two-sided CI for the least squares mean difference between groups will be calculated. To prove the 2 products to be biosimilar, the confidence limits for this difference have to be within the equivalence margin of ± 3.5 letters. The primary analysis for assessment of biosimilarity will be based on the primary estimand.

Interim analysis: When all subjects have completed their 6-month assessments, an unmasked analysis of efficacy and safety endpoints as well as PK and immunogenicity will be performed. The aim of the *unmasked* analysis is to initiate the submission of the application for marketing authorization as agreed with the European Medicines Agency. This analysis will not affect the further conduct of the study.

PK data: The PK data (plasma levels of ranibizumab) will be compared between 2 groups of subjects receiving Xlucane and Lucentis® in a statistical non-confirmatory manner, for comparative purpose.

Safety data: AEs will be coded using the Medical Dictionary for Regulatory Activities (MedDRA) and will be tabulated by system organ class (SOC) and preferred term (PT).

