AMD is divided into “early,” “intermediate,” and “late” types based on severity, with the late type being the most severe.² The late type can be further divided into the dry (atrophic) and the wet (ie, neovascular or exudative) forms. The dry form is less aggressive and accounts for 90% of all AMD cases but only for 10% of cases of blindness due to AMD. Dry AMD may develop into wet AMD. Wet AMD (wAMD) affects 10% of the AMD patients and is the more aggressive form, which, if untreated, leads to rapid severe visual impairment and in many cases, legal blindness.¹ However, 80% to 90% of patients with severe vision loss due to AMD have wAMD.¹

Wet AMD causes rupture of Bruch's membrane, an associated localized inflammatory response, and release of vascular endothelial growth factor (VEGF), which induces choroidal neovascularisation (CNV). The newly formed blood vessels grow through the ruptured membrane underneath the RPE and the retina. These new vessels are fragile and leak blood and proteins and may cause persistent edema below the macula, resulting in permanent damage to photoreceptors and the loss of central vision.

Treatment of wAMD includes photodynamic therapy (PDT) and laser coagulation, (although a recent Cochrane review found that laser coagulation is ineffective at preventing CNV and limiting loss of VA).⁴

To date, standard of care treatment for wAMD is intravitreal (IVT) anti-VEGF therapy, with the VEGF-antagonist pegaptanib (Macugen®; Bausch + Lomb) and the monoclonal antibody ranibizumab (Lucentis®; Genentech/Novartis). Another anti-VEGF treatment for wAMD is afibercept (Eylea®; Regeneron), which is a VEGF-trap that interferes with the biological actions by binding to VEGF-A, preventing it from interacting with its receptors.

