8 INVESTIGATIONAL PLAN

8.1 Overall Study Design and Plan: Description

This is a phase III multicenter, double-blind (double-masked), randomized, parallel group study in subjects with wAMD. Approximately 580 subjects will be enrolled and randomized in a 1:1 ratio to receive either Lucentis® (0.05 mL of 10 mg/mL ranibizumab) or the investigational product (IP), Xlucane (0.05 mL of 10 mg/mL ranibizumab), in the study eye once every 4 weeks for 52 weeks (ie, 12 months).

The study eye will be defined as the eye meeting all of the inclusion criteria and none of the exclusion criteria (ie, the enrollment criteria).

The assigned study drug will be administered as an ophthalmic intravitreal (IVT) injection. Designated, unmasked study staff will prepare and administer the study drug, ensuring that the masking of the subject is maintained during the injection procedure. See [Section 8.4.6](#).

Subjects will be randomized by interactive web response system (IWRS) to receive 13 doses of either Xlucane or Lucentis® in the study eye. The randomization scheme will automatically ensure that the study drug assignment for a given subject is random and that an overall 1:1 ratio of assignments to each of the 2 study drug treatments is approximated. In addition, the randomization scheme will include the following stratification parameters to ensure balanced distribution of assignment to the 2 treatments: eye color (light iris vs dark iris), geographical region where enrolled and the BCVA letters at Baseline (55 or lower, 56 to 65, 66 or higher). Subjects will be followed up for changes in efficacy variables and safety for 52 weeks. Each subject's involvement will last up to approximately 52 weeks (ie, 12 months).

[figure not shown]
At the beginning of the study, a subgroup of between approximately 40 and 60 subjects at a select number of participating sites will be sequentially asked to participate in an evaluation of PK. This subgroup will be asked to provide blood samples for measurement of plasma ranibizumab immediately before administration of the first dose of Xlucane or Lucentis®. Additional samples will be collected 23 hours after the first dose (ie, Day 1) and 23 hours after the sixth dose (ie, Week 20) at expected time to maximum plasma concentration (T_{max} , which is around 22 hours). The primary analysis set will be the Per-Protocol population.

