8.1.2 Schedule of Additional Assessments for PK Subgroup ONLY

Visit(s)	2	2b ²	8b ³
Time point	Day 0	Day 1 ²	(Week 20) ³
Blood Sampling Window (±)	≤ 60 minutes Predose	23 hours ± 60 minutes Postdose	23 hours ± 60 minutes postdose
Blood sample(s) for PK evaluation	X ¹	X	X ³
IOP measurement ⁴		X	X
SLE ⁵		X	X
Adverse event reporting		X	X

Abbreviations: IOP = intraocular pressure; PK = pharmacokinetic; SLE = slit lamp examination.

Notes:

1. Day 0 PK blood sampling must be performed ≤ 60 minutes before the first IVT injection of study medication.
2. Day 1 PK blood sampling must be performed 23 hours (± 60 minutes) after the IVT injection (ie, first dose of study medication).
3. Week 20 PK blood sampling must be performed 23 hours (± 60 minutes) after the IVT injection (ie, sixth dose of study medication).
4. IOP is measured by tonometry in the study eye only. Non-contact tonometry may be used, but in the event IOP is greater than 36 mm Hg, it is recommended to perform another IOP measurement with Goldmann or Tonopen or ICare (applanation tonometer) within the next 30 minutes.
5. Slit lamp examination of the anterior segment is conducted in the study eye only.

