11.3.5 Pharmacokinetics

The PK data analysis will be performed using the PK Set.

The ranibizumab PK concentrations will be summarised by treatment and listed individually. Descriptive statistics on the PK parameters ($C0$, predose; $C1$, time point 23 hours [\pm 60 minutes] after the first dose on Day 1; and $C6$, time point 23 hours [\pm 60 minutes] after the sixth dose on Week 20) will be presented. If a difference in ranibizumab protein concentration between Xlucane and Lucentis® batches is detected, additional descriptive statistics will be presented taking such difference into account. Further details will be defined in the statistical analysis plan.

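### Section 8.4.7 advises holding necessary fellow-eye anti-VEGF until after the Week 20 PK sample, with no safety qualifier and no limit to the PK subgroup

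*Combined protocol and SAP*

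**What the plan says.** Section 8.4.7 covers a fellow eye that develops AMD or another condition during the study. It first allows local treatment under the site's usual standard of care. It then adds: "If anti-VEGF therapy is necessary, it is recommended to start it no earlier than after the last PK assessment", and advises giving fellow-eye injections between study drug injections.

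The same section handles another deferral differently: "Ocular surgery to the study eye should be delayed until the subject completes the study, if possible and safe". It also gives a general query route: "If the permissibility of any medication/treatment is in question, please contact the medical monitor".

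PK sampling appears only under "Schedule of Additional Assessments for PK Subgroup ONLY" (Section 8.1.2): before the first dose, 23 hours after the first dose, and 23 hours after the sixth dose at Week 20. Section 8.1 describes "a subgroup of between approximately 40 and 60 subjects at a select number of participating sites"; the synopsis gives 60.

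The synopsis says PK will be compared "in a statistical non-confirmatory manner, for comparative purpose". Section 11.3.5 states: "The ranibizumab PK concentrations will be summarised by treatment and listed individually", with descriptive statistics and no acceptance criterion. Section 6.1 names intravitreal anti-VEGF as the standard of care for wet AMD, and says of the disease that it, "if untreated, leads to rapid severe visual impairment and in many cases, legal blindness".

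**The concern.** The condition in the sentence is that anti-VEGF is already judged necessary, and the advice is then to hold it until a sampling milestone. The section's authors attached a safety condition to deferring study-eye surgery but not to this deferral.

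The allowance for local standard of care does not resolve this when the fellow eye develops wet AMD, because on the protocol's own account that standard is the treatment being deferred. Section 6.1 also mentions photodynamic therapy and laser, but cites a review that found laser ineffective.

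The sentence is also unrestricted in scope. For subjects outside the subgroup there is no last PK assessment, so the natural reading is that it does not apply to them, but Section 8.4.7 does not say so.

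Under the Section 8.1.1 footnotes, scheduled slit lamp, dilated fundus and OCT examinations of the fellow eye stop after Day 0. A need arising before Week 20 would therefore probably come to light through symptoms; that is my inference.

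At stake is vision in the fellow eye of a few subjects, set against a PK value that does not enter the equivalence conclusion.

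**Working it through.** The plan gives no figure on this point. The steps below size the wait, the number affected, and what would be lost by not waiting.

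**1. Nominal wait.** The last PK sample is at 20 × 7 = 140 days plus 23 hours, about Day 141. Wait = 141 − 7 × (week in which need arises).

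| Need arises | Wait (days) | Wait (weeks) |
|---|---|---|
| Day 0 (theoretical limit) | 141 | 20.1 |
| Week 4 | 113 | 16.1 |
| Week 8 | 85 | 12.1 |
| Week 12 | 57 | 8.1 |
| Week 16 | 29 | 4.1 |

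The Day 0 row is a bound, not a case. Inclusion criterion 5 excludes a fellow eye expected to need anti-VEGF, and eligibility is reconfirmed on Day 0. For need arising after Day 1 the nominal wait is below 140 days, just under 20 weeks. Each visit is timed from the previous one (Sections 9.2.2 to 9.2.7), so permitted windows could move the Week 20 visit by up to 2 + 2 + 2 + 5 + 5 + 5 = 21 days either way.

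**2. Subjects with PK sampling.** 40/580 = 6.9% to 60/580 = 10.3%. The other 520 to 540 have no PK assessment.

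**3. Number affected.** The documents give no rate of fellow-eye need before Week 20, so I assume 0.5%, 2% and 5%. Expected number = rate × 40 to 60. If each such subject loses the Week 20 value and losses are spread evenly over the arms, the standard error of a PK mean is multiplied by √(1/(1 − rate)).

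| Assumed rate | PK subjects affected | Rise in standard error |
|---|---|---|
| 0.5% | 0.2–0.3 | 0.3% |
| 2% | 0.8–1.2 | 1.0% |
| 5% | 2–3 | 2.6% |

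PK is summarised by treatment, about 20 to 30 per arm. If at the 5% rate every loss fell in one arm (2 of 20, or 3 of 30), that arm's standard error would rise by √(20/18) − 1 = √(30/27) − 1 = 5.4%. Need arising after Day 1 cannot affect the pre-dose or Day 1 samples.

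**4. Does earlier treatment threaten the primary analysis?** Section 11.4 claims more than 90% power with 580 subjects, SD 10, margin ±3.5 letters and a 95% CI.

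- SE = 10 × √(2/290) = 0.830 and 3.5/0.830 = 4.215. At a true difference of zero, power = 2Φ(4.215 − 1.960) − 1 = 97.6%, or 97.54% with the variance estimated. The plan's claim is reproduced.
- With uniform onset and the 5% rate, the Week 8 values in PK subjects that would follow fellow-eye treatment number 40 to 60 × 0.05 × 8/20 = 0.8 to 1.2.
- Removing 1.2 subjects (N = 578.8) leaves power at 97.51%.

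The primary analysis gives no reason to wait.

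**The case against.** The strongest reply is that nothing blocks early treatment. The sentence recommends; it does not prohibit. The exceptions listed in Section 8.4.7 cover systemic anti-VEGF and investigational agents, not local fellow-eye anti-VEGF. Section 11.3.3.1 plans for a fellow-eye start as an intercurrent event, the medical monitor can be asked, and Section 8.3.5 lets a subject withdraw without prejudice to further care. Harm requires an investigator to follow optional advice against clinical judgement. All of this stands and keeps the point minor. It does not supply the missing qualifier: a query route about permissibility does not tell a site that necessary treatment need not wait.

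The PK motive is not stated; I infer it from the choice of milestone. Waiting past Week 20 would also keep fellow-eye treatment clear of the Week 8 endpoint, although that does not explain a Week 20 threshold. Avoiding added systemic anti-VEGF before the sample is a legitimate aim, since PK exposure is a secondary objective and Xlucane had no earlier clinical study.

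The rate of need is assumed, and at its low end nobody is affected. PK subjects are recruited at the start of the study, so some or all may already be past Week 20. The documents give no dates, so the benefit to them cannot be judged.

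A reader might infer that necessary treatment is forbidden until Week 20, that a 20-week wait from Day 0 is a realistic case, or that all 580 subjects are held back. The documents support none of these: the wording is advisory, criterion 5 screens out need foreseen at entry, and PK sampling exists only in the subgroup.

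**Conclusion.** The concern holds as a minor patient-safety point. As written, Section 8.4.7 advises postponing necessary fellow-eye anti-VEGF to a PK milestone, without a safety condition or a stated limit to PK subjects, and it conflicts with the preceding sentence when the fellow eye has wet AMD. The nominal wait depends only on the visit schedule and the time of onset. The count of 0.2 to 3 affected PK subjects rests entirely on the assumed 0.5% to 5% rates. What the wait protects is, at most, the same number of Week 20 values in a non-confirmatory summary. The equivalence conclusion and sample size are not in question.

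**What to change.** Replace the sentence in Section 8.4.7 with wording such as:

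> *For PK-subgroup subjects only, fellow-eye anti-VEGF should preferably start after the Week 20 PK sample if, in the investigator's judgement, waiting poses no risk to vision; otherwise, and in all non-PK subjects, it should start when clinically indicated.*

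Keep the advice to give fellow-eye injections between study drug injections.

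Add to Section 11.2 that PK samples taken after the start of fellow-eye anti-VEGF are flagged as non-evaluable whether or not a protocol deviation is recorded. The present flagging rule is triggered by a deviation, and treatment the protocol expressly allows would not be one. That would leave only the general discretion of the blinded data review meeting.

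The cost is one sentence in each section and a letter to sites. The downside is the possible loss of a few descriptive Week 20 values, with the loss of precision shown in the working.
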